5.3 SCREEN FAILURES

Screen failures are defined as participants who consent to participate in the clinical trial but are not subsequently randomly assigned to the study intervention or entered in the study. A minimal set of screen failure information is required to ensure transparent reporting of screen failure participants, to meet the Consolidated Standards of Reporting Trials (CONSORT) publishing requirements and to respond to queries from regulatory authorities. Minimal information includes demography, screen failure details, eligibility criteria, and any serious adverse event (SAE).

Individuals who do not meet the criteria for participation in this trial (screen failure) because of a may be rescreened. Rescreened participants should be assigned the same participant number as for the initial screening.

5.4 STRATEGIES FOR RECRUITMENT AND RETENTION

Potential subject for this trial will be recruited from all patients with mild TBI (GCS 13-15) presenting within 7 days of injury to the University of Michigan Emergency Department. Trained research personnel will perform enrollment of subjects.

Target sample size: 50 participants

Anticipated accrual rate: 5-10 patients per month

Anticipated number of sites: 1

Source of participants: Emergency Department and Inpatient admissions of the University Hospital, University of Michigan

How potential participants will be identified and approached: Trained research coordinators will screen the Emergency Department Dashboard of MiChart for eligible patients. They will then approach emergency physicians/physician assistants taking care of eligible patients and ask for permission to approach their patient to further discuss the study and obtain informed consent. This will occur in the emergency department. If the potential subject agrees to the referral, the research coordinator will approach the potential subject and begin the consent process. This process will help maintain patient privacy, by allowing potential subjects to have control over who has access to them. For patients lacking the capacity to consent, an authorized legal representative will be identified for consent purposes. Participation in the study will be voluntary.

Incentives for visit attendance: A cash incentive of \$75 will be provided for attending the 2 week visit, \$75 for attending the 1 month visit and \$150 for attending the 3 month visit.

Inclusion of women and minorities: Traumatic brain injury occurs more frequently in men. However, efforts will be made to ensure that all eligible women are included. Additionally, efforts will be made to ensure an adequate representation of under-represented minorities.

6 STUDY INTERVENTION

6.1 STUDY INTERVENTION(S) ADMINISTRATION

6.1.1 STUDY INTERVENTION DESCRIPTION

The study intervention is an omega-3 fatty acid capsules manufactured by Wiley's Finest. We will utilize a formulation that contains 500 mg of docosahexaenoic acid (DHA) and 100 mg of eicosapentaenoic acid (EPA) in one capsule

6.1.2 DOSING AND ADMINISTRATION

Every attempt will be made to start treatment as soon as possible after enrollment. The first dose will be administered within 7 days of injury. The intervention group will receive 6g per day of DHA+EPA for 1 month followed by 1.2 g/day of EPA+DHA for two additional months. The control group will receive placebo treatment for 3 months.

6.2 PREPARATION/HANDLING/STORAGE/ACCOUNTABILITY

6.2.1 ACQUISITION AND ACCOUNTABILITY

Study medications will be acquired from Wiley's Finest and stored and dispensed by the University of Michigan Research Pharmacy Group

6.2.2 FORMULATION, APPEARANCE, PACKAGING, AND LABELING

Study medication will be supplied as soft-gelatin capsules filled with light-yellow oil.

6.2.3 PRODUCT STORAGE AND STABILITY

- Store study medications at room temperature between 68°F to 77°F (20°C to 25°C).
- Do not freeze study medication
- Safely throw away medicine that is out of date or no longer needed

6.2.4 PREPARATION

The study drug will not need additional preparation

6.3 MEASURES TO MINIMIZE BIAS: RANDOMIZATION AND BLINDING

A web-based central randomization system will be developed and utilized. Study team members will be blinded to study group allotment.

6.4 STUDY INTERVENTION COMPLIANCE

Adherence to protocol will be assessed by measuring plasma levels of EPA and DHA and red blood cell index of omega-3 fatty acids at each follow-up visit.

7 STUDY INTERVENTION DISCONTINUATION AND PARTICIPANT DISCONTINUATION/WITHDRAWAL

7.1 DISCONTINUATION OF STUDY INTERVENTION

Discontinuation from taking the study medication does not mean discontinuation from the study, and remaining study procedures should be completed as indicated by the study protocol. If a clinically significant finding is identified (including, but not limited to changes from baseline) after enrollment, the investigator or qualified designee will determine if any change in participant management is needed. Any new clinically relevant finding will be reported as an adverse event (AE).

The data to be collected at the time of study intervention discontinuation will include the following:

- Blood samples, functional, symptomatic and cognitive outcomes data

7.2 PARTICIPANT DISCONTINUATION/WITHDRAWAL FROM THE STUDY

Participants are free to withdraw from participation in the study at any time upon request.

An investigator may discontinue or withdraw a participant from the study for the following reasons:

- Pregnancy (self-reported)
- Significant study intervention non-compliance
- If any clinical adverse event (AE), laboratory abnormality, or other medical condition or situation occurs such that continued participation in the study would not be in the best interest of the participant
- Disease progression which requires discontinuation of the study intervention
- If the participant meets an exclusion criterion (either newly developed or not previously recognized) that precludes further study participation
- Participant unable to receive the study medication for 2 weeks or more

The reason for participant discontinuation or withdrawal from the study will be recorded on the Case Report Form (CRF). Subjects who sign the informed consent form and are randomized but do not receive the study intervention may be replaced. Subjects who sign the informed consent form, and are randomized and receive the study intervention, and subsequently withdraw, or are withdrawn or discontinued from the study, will be replaced.

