1 PROTOCOL SUMMARY

1.1 SYNOPSIS

Title:	Pilot Study of Omega-3 Polyunsaturated Fatty Acid Treatment in Mild Acute TBI (OPTIMA-TBI pilot).
Study Description:	This is a double-blinded randomized control trials comparing the effect of omega-3 fatty acid versus placebo on blood biomarkers of brain injury, inflammation and neurogenesis.
Objectives:	
Primary Objective: Biomarker endpoints include: neuronal injury measured by Neurofilament light chain (NFL), Neurogranin (NRGN) and Intercellular adhesion molecule 5 [ICAM5]; inflammation measured by high sensitivity C-reactive protein (CRP), IL-6 and IL-10 and neurogenesis measured by brain derived neurotrophic factor (BDNF)
 
Secondary Objectives:
 
1. Delayed functional recovery defined as Glasgow Outcome Scale Extended (GOSE)<8 at 3 months2. Moderate/severe post-concussive symptoms at 3 months defined as having at least three symptoms in at least three following ICD-10 symptom categories obtained from the Rivermead Post-Concussion Questionnaire (RPQ): (1) headaches, dizziness, general malaise, excessive fatigue, or noise intolerance; (2) irritability, emotional lability, depression, or anxiety; (3) subjective complaints of concentration or memory difficulty; (4) insomnia; (5) reduced tolerance to alcohol; (6) preoccupation with these symptoms and fear of permanent brain damage.3. Cognitive impairment at 3 months is defined based on a battery of 13 neurocognitive tests. Subjects are deemed cognitively impaired if their scores on at least 2 neurocognitive tests are more than 2 standard deviations below their IQ T-Score ascertained by the Wechsler Test of Adult Reading (WTAR).4. Serious adverse events (SAEs): Life-threatening bleed including upper GI bleed, intracranial hemorrhage; hypotension; severe allergic reaction, blood glucose and LDL cholesterol levels
Endpoints:	
Primary Endpoint: Serum levels of neurofilament light chain, C-reactive protein, IL-6, IL-10, Brain derived neurotrophic factor over a 3-month period
 
Secondary Endpoints: Functional recovery (measured by Glasgow Coma Scale Extended), symptomatic recovery (measured by the Rivermead Post-concussive Symptoms Questionnaire) and cognitive impairment (measured by a cognitive battery) at 3 months post injury

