1.2 SCHEMA

1.3 SCHEDULE OF ACTIVITIES (SOA)

Activity	Enrollment	2 week visit	1 month visit	3 month visit
Screening	X			
Demographics	X			
Medical History	X			
Pre-hospital Events	X			
Informed consent	X			
Clinical data elements	X			
Rivermead Post-Concussion Questionnaire	X	X	X	X
Blood draw	X	X	X	X
Study medication	X	X	X	X
Glasgow Outcome Scale Extended		X	X	X
Montreal Cognitive Assessment			X	X
Brief Test of Attention (BTA)			X	X
Trail Making Test, Part A, Part B			X	X
Stroop Test			X	X
Controlled Oral Word Association Test (COWAT)			X	X
Wisconsin Card Sorting Test (WCST)			X	X
Hopkins Verbal Learning Test (HVLT)			X	X
Brief Visual Memory Test (BVMV)			X	X
Wechsler Test of Adult Reading (WTAR)			X	X
Patient Health Questionnaire 9 (PHQ9)			X	X
Generalized Anxiety Scale GAD 7			X	X
Davidson Trauma Scale to assess PTSD			X	X
Pittsburg Sleep Questionnaire			X	X
Satisfaction with life scale			X	X
Social Ties Check List			X	X
McGill pain scale			X	X

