4 STUDY DESIGN

4.1 OVERALL DESIGN

We hypothesize that treatment of traumatic brain injury patients with omega-3 fatty acids will result in a decrease in blood concentrations of biomarkers of neuronal injury and inflammation and an increase in the blood concentration of biomarkers of neurogenesis. This is a randomized, placebo-controlled, double-blinded pilot phase II clinical trial. Participants will be randomized either a single dose of 6g of DHA+EPA for 1 month followed by 1.2g/day of DHA+EPA for two additional months or to placebo treatment for 3 months. Blood samples will be drawn at enrollment, 2 weeks, 1 month and 3 months post-injury. Biomarkers of neuronal injury, inflammation, and neurogenesis will be measured in batches. Functional and symptomatic recovery will be assessed at 2 weeks, 1 month and 3 months. Additionally, cognitive impairment will be assessed at 3 months.

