5.2 EXCLUSION CRITERIA

Subjects will be excluded if they have any of the following findings:

1. GCS<13 at any time during ED stay.
2. Significant polytrauma including: bony fracture or solid organ injury
3. Study medication cannot be administered within 7 days of injury
4. Patient cannot be relied on to complete follow-up (i.e. no reliable telephone number, substance dependence, homeless)
5. Cannot communicate in English
6. Take an anticoagulant (coumadin or a novel oral anticoagulant) daily
7. Age less than 18 years or greater than 65 years
8. Patients already taking fish oil supplements daily
9. History of cognitive impairment
10. Allergic to fish/fish oil
11. Pregnant women (self-reported)

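### Section 7.2 permits withdrawal from the study, with replacement, for disease progression or a later-arising exclusion criterion, which allows outcome-related removal after randomisation and conflicts with section 7.1

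*Combined protocol and SAP*

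**What the plan says.** Section 7.2 opens its list with "An investigator may discontinue or withdraw a participant from the study for the following reasons". Two entries matter here: "Disease progression which requires discontinuation of the study intervention" and "If the participant meets an exclusion criterion (either newly developed or not previously recognized) that precludes further study participation". The same section then says that participants who were randomised and treated "and subsequently withdraw, or are withdrawn or discontinued from the study, will be replaced". So withdrawal is at the investigator's discretion, but replacement of a treated participant is not.

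Section 7.1 takes a different line on stopping study medication. It says that this is not the same as leaving the study, that the remaining procedures should be completed, and that blood samples and functional, symptomatic and cognitive data are collected when medication stops.

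Exclusion 9 in section 5.2 reads "History of cognitive impairment", with no definition, threshold or time reference. The synopsis makes cognition a secondary endpoint: "Cognitive impairment at 3 months is defined based on a battery of 13 neurocognitive tests". Section 4.1 gives the timing as "Additionally, cognitive impairment will be assessed at 3 months". The schedule in section 1.3, however, marks the cognitive tests at 1 month as well as at 3 months. Functional and symptom scales are collected from 2 weeks.

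Section 9.4.1 names no analysis population and does not say how withdrawn or replaced participants are handled. Intention-to-treat appears only in the abbreviation list (section 10.2).

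**The concern.** Randomisation protects the comparison only if everyone randomised is followed and counted. Progression after a brain injury is plausibly linked to poor functional, symptomatic and cognitive recovery, which are the secondary endpoints. If progression can end study participation, and the place goes to a new participant, the people most likely to have a poor 3-month result can leave the data. Their later blood samples leave too, and the primary hypothesis in section 9.1 concerns biomarker curves over the full 3 months.

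Two consequences follow. If the same share of poor outcomes leaves each arm, observed event rates fall in both and a true difference shrinks. If the shares differ, a difference can appear where there is none. Section 3 says these endpoints are meant to inform the design of a multi-center phase II trial, so rates depleted of poor outcomes would feed directly into its planning.

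**Working it through.** **Reading the text.** Three steps show that the route is open.

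1. Progression leads to stopping the intervention, which 7.2 makes a permitted reason to leave the study. Section 7.1 says that stopping medication does not mean leaving. One section sets continued follow-up as the default; the other permits the opposite in the same situation.
2. Once a treated participant is withdrawn under 7.2, replacement follows whatever the reason.
3. Nothing in section 9 restores the person to the analysis.

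The cognitive route needs an extra step. Exclusion 9 is a history item, and it must be combined with the wording in 7.2 on criteria that develop later. Because exclusion 9 has no time limit, that combination is possible, but it is not the natural reading.

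**Size (illustration only).** The plan has no figure to reproduce. Section 9.2 gives 50 patients without an event rate, allocation ratio or dropout rate, and no withdrawal rate is stated anywhere. The assumptions are:

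- *p* is the true 3-month impairment rate in an arm.
- *w* is the share of impaired participants who are withdrawn.
- Those withdrawn would still have been impaired at 3 months.
- Replacements come from the same population and face the same rule.

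The observed rate among those retained is *p*(1 − *w*) / (1 − *pw*).

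With true rates of 30% (control) and 15% (omega-3):

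- *w* = 0: 30.0% vs 15.0%, difference 15.0 points.
- *w* = 0.25: 0.225/0.925 = 24.3% vs 0.1125/0.9625 = 11.7%, difference 12.6 points.
- *w* = 0.50: 0.15/0.85 = 17.6% vs 0.075/0.925 = 8.1%, difference 9.5 points, about 36% smaller than the truth.

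Other assumed rates behave in the same way. For 20% vs 10%, the 10.0-point difference becomes 8.1 (*w* = 0.25) or 5.8 (*w* = 0.50). For 40% vs 20%, 20.0 points becomes 17.5 or 13.9.

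With no treatment effect and 30% in both arms:

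- Equal *w*: the observed rates are equal, so no false difference appears.
- *w* = 0 vs 0.50: 30.0% − 17.6% = a false difference of 12.4 points.
- *w* = 0.25 vs 0.50: 24.3% − 17.6% = 6.7 points.

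The formula describes whoever completes, with or without replacement. Replacement leaves the expected rates unchanged; it refills the arm, so the number completing no longer shows the loss.

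**The case against.** A reader might infer that the exclusion list contains cognitive impairment as such, so that anyone found impaired at 1 month would be removed before the 3-month endpoint. The documents do not support that. The item is a *history* of impairment, which ordinarily screens for a pre-existing condition. Withdrawal is discretionary, and the criterion must be one that rules out continuing. No section says that a low score does so, that the two-of-13 rule in section 8.1 is scored at 1 month, or that 1-month scores guide withdrawal. This limits the cognitive route to an unlikely one, left open by loose wording.

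The progression item is also qualified: it applies only where the intervention has to stop, and no section ties a poor functional or symptom score to stopping. Section 7.1 does protect follow-up after stopping. But it governs stopping medication and does not override the power to withdraw in 7.2, so the conflict remains.

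Section 6.3 blinds the study team and 7.2 records withdrawal reasons on the case report form. Blinding makes selection on knowledge of arm less likely, and the recorded reasons would let such removals be seen. Neither prevents selection on an observed course of illness.

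Finally, this is a small pilot. At an assumed 25 per arm and 30% vs 15%, the standard error of the difference is √(0.30×0.70/25 + 0.15×0.85/25) = 11.6 points. The 5.5-point loss at *w* = 0.50 (15.0 − 9.5) is under half of that, and section 9.4.1 specifies no test of the cognitive endpoint. That is fair as regards inference within this trial. It does not help the planning use: a control rate read as 17.6% instead of 30% is a systematic error, and a larger sample would not remove it.

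**Conclusion.** The concern holds in a limited form. As written, 7.2 permits removal and replacement of randomised participants for reasons plausibly related to outcome. Its progression item conflicts with 7.1, and no analysis set keeps those removed. Disease progression is the main route; the history criterion is a secondary and less likely one.

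The documents do not show that such removals are required or expected, or that they would differ by arm. A reader might conclude that the plan discards its worst outcomes or will produce a biased treatment comparison; that goes further than the text. The range of 12.6 to 9.5 points for a true 15 rests entirely on assumed event rates, on assumed withdrawal shares of 25% to 50%, and on impairment persisting to 3 months. A false difference needs unequal shares.

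**What to change.** Revise section 7.2, and reconcile it with 7.1, to state that:

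- eligibility criteria are applied at enrolment;
- exclusion 9 means a history before the index injury;
- an exclusion criterion that arises or is discovered after randomisation, or disease progression, does not by itself end outcome follow-up;
- these participants complete the remaining scheduled visits unless they withdraw consent or continued participation is judged not to be in their best interest;
- all are analysed in their assigned arm, which section 9.4.1 should repeat;
- any replacements are added to those already randomised, not substituted for them.

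Decisions about study medication stay with section 7.1 and the clinician and are not touched by this change. The cost is protocol wording and a few follow-up visits that are already scheduled, with no new procedures.

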7.3 LOST TO FOLLOW-UP

A participant will be considered lost to follow-up if he or she fails to return for a scheduled visit and is unable to be contacted by the study site staff.

The following actions must be taken if a participant fails to return to the clinic for a required study visit:

- The site will attempt to contact the participant and reschedule the missed visit within 2 weeks and counsel the participant on the importance of maintaining the assigned visit schedule and ascertain if the participant wishes to and/or should continue in the study.
- Before a participant is deemed lost to follow-up, the investigator or designee will make every effort to regain contact with the participant (where possible, 3 telephone calls and, if necessary, a certified letter to the participant's last known mailing address or local equivalent methods). These contact attempts should be documented in the participant's medical record or study file.
- Should the participant continue to be unreachable, he or she will be considered to have withdrawn from the study with a primary reason of lost to follow-up.

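### Section 7.2 allows withdrawal from the study for medication reasons alone and replaces treated leavers without saying the originals stay in the analysis, so 3-month outcomes can be lost after randomisation

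*Combined protocol and SAP*

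**What the plan says.** Section 7.1 sets the default: "Discontinuation from taking the study medication does not mean discontinuation from the study, and remaining study procedures should be completed". It also lists data to collect when medication stops: "Blood samples, functional, symptomatic and cognitive outcomes data".

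Section 7.2 deals with leaving the study: "An investigator may discontinue or withdraw a participant from the study for the following reasons". Two of the listed reasons concern capsule intake and nothing else: "Significant study intervention non-compliance" and "Participant unable to receive the study medication for 2 weeks or more". The section then says that subjects who are "randomized and receive the study intervention, and subsequently withdraw, or are withdrawn or discontinued from the study, will be replaced". For those randomised but never treated, replacement is optional.

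Section 7.3 brings the unreachable participant under the same rule: "he or she will be considered to have withdrawn from the study with a primary reason of lost to follow-up".

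On timing, Section 4.1 says "Blood samples will be drawn at enrollment, 2 weeks, 1 month and 3 months post-injury". The primary hypothesis in 9.1 is an area under the concentration curve (AUC) over the 3 months after injury. The synopsis places the functional, symptom and cognitive endpoints at 3 months. Section 9.3 compares biomarkers at baseline and 3 months and fits a GEE model to the repeated biomarker values. Sections 9.1 to 9.3 define no analysis set, give no rule for missing data and do not mention replaced participants. Intention-to-treat appears only in the abbreviation list. Sections 3, 5.4 and 9.2 all give 50 participants, without saying whether that counts those randomised or those who complete.

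**The concern.** The 3-month visit carries most of what this trial wants to learn, and 7.2 allows it to be given up because of what happened to the capsules after randomisation. Someone who is non-adherent or off medication can be kept under 7.1 or withdrawn under 7.2, and no text says which section governs. *Significant* non-compliance is undefined. The choice is therefore a discretionary event after randomisation, and it may relate both to treatment (through tolerability) and to recovery.

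The adherence measure gives a further route to imbalance. Section 6.4 relies on omega-3 blood levels. These can flag missed capsules in the active arm but say little about adherence to olive oil. The documents do not say that these results feed the non-compliance ground, but nothing excludes it.

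Section 4.2 justifies the design by the unbiased comparison that randomisation gives. That holds only if outcomes are sought from everyone randomised. Enrolling a replacement restores the headcount but not the missing outcome.

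**Working it through.** **No plan figure to reproduce.** The sample size of 50 is given without alpha, power, effect size, SD or dropout, and no withdrawal rate appears anywhere. Everything below is illustrative.

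**Assumed inputs.** No true effect; 25 analysed per arm (the documents state no allocation ratio); removal from all causes of 20% in the active arm and 8% on placebo; removal driven by a normal liability correlated c = 0.3 to 0.5 with a worse 3-month value; within-person correlation rho = 0.5 to 0.7 between visits.

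**1. Leavers' data dropped, continuous 3-month outcome.** The bias is d = c × [φ(z_a)/(1−q_a) − φ(z_p)/(1−q_p)], where q is the proportion removed in the arm and z the matching normal quantile.
- Active arm: 0.2800/0.80 = 0.3500. Placebo arm: 0.1487/0.92 = 0.1616. Difference: 0.1884.
- d = 0.3 × 0.1884 = 0.057 SD, or 0.5 × 0.1884 = 0.094 SD.
- SE = √(2/25) = 0.283 SD, so d/SE = 0.20 to 0.33.
- Two-sided type I error at a nominal 5%: 5.5% to 6.3%.
- With 20% v 10%: 0.047 to 0.078 SD. With 20% v 20%: zero.

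A cruder model, in which leavers differ from stayers in their own arm by g SD, gives (q_a − q_p) × g. For g = 0.5 to 1.0, 20% v 5% gives 0.08 to 0.15 SD and 30% v 10% gives 0.10 to 0.20 SD. The size follows the inputs.

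**2. Earlier visits kept in the GEE (exchangeable correlation).** With k earlier samples, the 3-month bias is d × [1 − kρ²/(1+(k−1)ρ)].
- Largest (k = 2, ρ = 0.5, c = 0.5): 0.094 × 0.667 = 0.063 SD.
- Smallest (k = 3, ρ = 0.7, c = 0.3): 0.057 × 0.3875 = 0.022 SD.
- Adding the 7.1 discontinuation sample as one more predictor (k = 3 or 4): 0.021 to 0.059 SD. It helps little, because it is not a 3-month value.

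**3. AUC.** With visits at days 0, 14, 30.4 and 91.3, the 3-month sample has trapezoid weight (60.9/2)/91.3 = 33%, and the last interval is 60.9/91.3 = 67% of the window. Enrolment may be as late as day 7 after injury; then the window is 84.3 days and the figures are 36% and 72%. Taking enrolment at day 0, the correlation of the 3-month value with the AUC is 0.819 (ρ = 0.5) or 0.896 (ρ = 0.7). A completers' AUC is then biased by 0.057 × 0.819 = 0.046 to 0.094 × 0.896 = 0.084 SD. With earlier visits kept, the AUC of visit means is biased by about 0.01 to 0.03 SD.

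**4. Binary 3-month clinical outcome, retained participants only** (bivariate normal liability, same true rate in both arms):

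| True rate | False difference, c = 0.3 | c = 0.5 | SE = √(2p(1−p)/25) |
|---|---|---|---|
| 30% | 2.1 points | 3.6 points | 13.0 points |
| 40% | 2.3 | 4.0 | 13.9 |
| 50% | 2.3 | 4.0 | 14.1 |

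**5. Replacement.** If treated leavers are replaced until 50 remain, the number randomised is 50/(1−d), with d now the overall leaving rate: 10% gives 55.6, so 56; 20% gives 62.5, so 63. That leaves 6 or 13 randomised participants without an assured 3-month outcome.

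**The case against.** The two sections do not strictly contradict each other. Section 7.1 is about stopping the intervention and 7.2 about leaving the study. Section 7.2 says *may*, and one of its two medication grounds has a stated threshold. An investigator could satisfy both by never using the discretion. That is right: what stands is an unreconciled discretion, and the loss of outcomes is possible, not certain.

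A reader might infer that the plan excludes leavers and compares completers only. The documents do not say so. They are silent, and the GEE in 9.3 could use leavers' earlier biomarker visits. But 9.3 describes that model for biomarkers only, so it gives no help with the 3-month clinical endpoints.

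A reader might also blame replacement for the bias. The bias comes from the missing outcomes; replacement merely fails to repair it and blurs who is to be analysed.

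The strongest objection is about size. The 20% v 8% covers removal for every cause. Voluntary withdrawal, loss to follow-up and the other 7.2 grounds would remain after the change, so the figures overstate what it can remove under that scenario. They are also small against the standard error of a 50-participant pilot with no stated power. This is accepted and limits the severity.

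**Conclusion.** The point holds as a cheap improvement of low-to-moderate severity. As written, 7.2 can end follow-up because of medication intake alone, and nothing in Section 9 secures the place of those participants in the analysis. On the assumed scenario, the distortion is at most about a third of a standard error for a continuous 3-month outcome, and less if earlier visits are used. For a binary endpoint it is 2-4 points against an SE of 13-14. It vanishes if removal and selection are the same in both arms.

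The documents do not support calling this a large bias or a demonstrated one. The case rests on an avoidable loss that cannot be made good later, in a pilot whose secondary endpoints are meant, according to Section 3, to inform a larger multi-centre trial.

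**What to change.** 1. Reconcile 7.1 and 7.2 so that being off study medication or non-adherent does not by itself end follow-up visits while the participant still consents. This concerns outcome collection only; decisions on stopping the capsules are not addressed.
2. State in Section 9 that all randomised participants are analysed in their assigned arm with all available visits.
3. Choose one rule for replacement:
   - (a) delete replacement of treated participants, so that 50 is the number randomised; or
   - (b) keep it, state that replacements are additional and never substitute for the originals, and accept that more than 50 may be randomised. Sections 3, 5.4 and 9.2 should then say what 50 counts.

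   The two cannot be combined: replacements are not additional if 50 is also the total randomised.

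**Cost.** An amendment needing IRB approval, plus some 3-month visits, samples and incentive payments ($150 each under Section 5.4) for participants who would otherwise have been withdrawn. Under (a), somewhat fewer than 50 may have complete 3-month data.
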